## STUDY SYNOPSIS

Sponsor / Sponsor- Investigator	PD Dr. med. [name]
Study Title:	Effects of photodynamic therapy on the human inguinal skin microbiome to improve antiseptic Effect – a pilot study
Short Title / Study ID:	Effects of photodynamic treatment on skin microbiome (PHOMIC)
Protocol Version and Date:	v04, 14.1.2020
Trial registration:	Bundesamtes für Gesundheit: www.kofam.ch. SNCTP000003386 International trial registry ClinicalTrials.gov (clinicaltrials.gov) NCT04067843
Study category and Rationale	Other clinical study Category A
Background and Rationale:	Periprosthetic joint infections are a feared complication after orthopedic surgery in particular in our increasing elderly population. These infections are usually difficult to treat, because microorganisms persist in biofilms on the orthopedic implant surface. Therefore, it would be desirable to prevent these infections. It is hypothesized that bacteria from the skin surface or dermis - such as Staphylococcus aureus , coagulase-negative staphylococci, or Cutibacterium sp. - are transmitted into the periimplant tissue during surgery. In a ongoing interdisciplinary study with the Orthopedic University Hospital Balgrist (data in preparation for publication), we see that common skin antisepsis preparation is not effective to eliminate skin bacteria before surgery because they persist in sebaceous or sweat glands. Photodynamic treatment (PDT) has recently gained attention in the treatment of acne, a disease of the pilosebaceous unit, in which also Cutibacterium acnes is implicated. The PDT works here on the one hand through a long-lasting destruction of the sebaceous glands, and on the other hand due to anti-inflammatory and antimicrobial effects.
Objective(s):	The overarching aim of this research project is to prevent orthopedic implant-associated infections. This study aims to investigate if photodynamic therapy has an effect on bacterial skin colonization and decrease number of colonizing bacteria associated with sebaceous and sweat glands in order to improve skin antisepsis strategies for the prevention of surgical site infections.

Outcome(s):	
Primary outcome
 
 
1. Immediate effect of photodynamic treatment in combination with surgical antisepsis on bacterial skin colonization           
 
1.1. To quantitatively evaluate bacterial density and species before photodynamic treatment and after photodynamic treatment and antisepsis skin preparation
 
 
 
2. Long-term effect on bacterial skin colonization in the groin after photodynamic treatment           
 
2.1. To quantitatively evaluate bacterial density and species before and after photodynamic treatment (7 and 21 days)
 
2.2. To evaluate changes of sebaceous and sweat glands after photodynamic treatment on skin biopsies
 
 
 
 
Secondary outcome
 
 
3. To evaluate phylogenetic similarity of the microbiota on the dermis before and three weeks following photodynamic treatment
 

Study design:	Pilotstudy, open label, single center
Inclusion / Exclusion criteria:	
Inclusion criteria
 
Healthy male and female participants <math>\geq 18</math> years who
 
 
• volunteer for the pilot study in which a routine photodynamic treatment in the Department of Dermatology will be applied and effect of skin colonization will be analyzed, and
 
• an informed consent is signed by the participant (after information about the project).
 
 
Exclusion criteria
 
 
• Pregnant and lacting women
 
• Participants with inability to follow the procedures of the study, e.g. due to language problems, psychological disorders, dementia, etc.,
 
• Participants taking antibiotics in the 14 days prior to the photodynamic treatment or until follow-up at 21 days
 
• Participants who received oral retinoid therapy within the last 6 months
 
• Participants who received anti-inflammatory agents as NSAR within the 14 days prior and after the PDT
 
• Participants taking any photosensitizing drugs within 4 weeks prior to the photodynamic treatment (PDT)
 
• Participants who had a history of photosensitivity disorder
 
• Fitzpatrick's skin phototype V-VI
 

Study Intervention:	
 
• Photosensitizer application, followed by fluorescence photography and photodynamic therapy (PHT) (1x) over 15 minutes at the dermatology ward
 
• Skin swabs
 
• Skin biopsies in only 5 participants
 

Reference Intervention:	From a current prospective study at the University Hospital Balgrist, we have the reference database of colonizing bacteria in the groin without photodynamic treatment. In addition, we will take skin swabs before and after skin antisepsis without antisepsis in 10 participants.
Number of Participants with Rationale:	Aim: 20 volunteers There will be only descriptive statistics to see if numbers of colonizing bacteria are decreased with photodynamic treatment to plan a clinical trial in patients getting a hip joint arthroplasty and previous antisepsis.
Study Duration:	1 year
Study Schedule:	
 
• Project start (FPFV): July 2019 
 
◦ First participant: July 2019
 
◦ Last participant: June 2020
 
 
 
• Project end (LPLV): July 2020
 

Investigator(s):	
[name] Division of Infectious Diseases and Hospital Hygiene University Hospital Zurich [name] Email: [contact] [contact]
 
Dr. med [name] Department of Dermatology University Hospital of Zurich, Zurich University Hospital Zurich [name] Email: [contact] [contact]

Study Centre(s):	Single-center
Statistical Considerations:	Categorical data will be tested for differences using Fisher's exact or chi-squared tests, as appropriate, whereas continuous variables will be tested using Wilcoxon rank sum tests.
GCP Statement:	This study will be conducted in compliance with the protocol, the current version of the Declaration of Helsinki, the ICH-GCP as well as all national legal and regulatory requirements.

## LIST OF ABBREVIATIONS

AE	Adverse Event
ClinO	Clinical Trial Ordinance (KlinV)
CRF	Case Report Form
eCRF	Electronic Case Report Form
GCP	Good Clinical Practice
ICH	International Council on Harmonization
ISF	Investigator Site File
PI	Principal Investigator
SAE	Serious Adverse Event
SDV	Source Data Verification
SNCTP	Swiss National Clinical Trial Portal
SOP	Standard Operating Procedure
TMF	Trial Master File
PJI	Periprosthetic Joint Infection
C. avidum	Cutibacterium avidum
CNS	Cogulase-negative staphylococci
Sp.	Species
CEC	Competent Ethics Committee
PDT	Photodynamic therapy
MAL	Methyl aminolevulinate
NSAR	Non-steroidal anti-inflammatory drugs

## **1.6 Monitoring Institution**

Since we only measure microbiological data from skin samples, we think, that an interne monitoring would be adequate. See chapter 12.3.

# **ETHICAL AND REGULATOR ASPECTS**

Before this study will be conducted, the protocol, the proposed participant information and consent form as well as other study-specific documents will be submitted to a properly constituted Competent Ethics Committee (CEC) in agreement with local legal requirements, for formal approval.

The decision of the CEC concerning the conduct of the study will be made in writing to the Sponsor-Investigator before commencement of this study. The clinical study can only begin once approval from the CEC has been received.

## **1.7 Study Registration**

The study will be registered in the Swiss Federal Complementary Database („Portal“) (Registry of ongoing Research Projects (RoPS)) and in the international trial registry ClinicalTrials.gov (clinicaltrials.gov).

## **1.8 Categorization of the Study**

**Category A:** The health-related study intervention (PTD, taking biopsies) entails only minimal risks and burdens.

## **1.9 Competent Ethics Committee (CEC)**

Approval from the appropriate constituted Competent Ethics Committee is sought for the clinical trial. The reporting duties and allowed time frame are respected. No substantial amendments are made to the protocol without prior CEC approval, except where necessary to eliminate apparent immediate hazards to study participants. Premature study end or interruption of the study is reported within 15 days. The regular end of the study is reported to the CEC within 90 days, the final study report shall be submitted within one year after study end. Amendments are reported according to chapter 2.9.

## **1.10 Ethical Conduct of the Study**

The study will be carried out in accordance with principles enunciated in the current version of the Declaration of Helsinki, the guidelines of Good Clinical Practice (GCP) issued by ICH, and Swiss competent authority's requirements.

CEC will receive annual safety and interim reports and be informed about non-substantial amendments, the course of the study, and the study stop/ end in agreement with local requirements.

## **1.11 Declaration of Interest**

No conflict of interest

## **1.12 Participant Information and Informed Consent**

The investigator must explain to each Participant the nature of the study, its purpose, the procedures involved, the expected duration, the potential risks and benefits and any discomfort it may entail. Each participant must be informed that the participation in the study is voluntary and that he/she may withdraw from the study at any time and that withdrawal of consent will not affect his/her subsequent medical treatment.

The participant must be informed that his/her medical records may be examined by authorized individuals other than their treating physician.

All participants for this study will be provided a participant information sheet and a consent form describing this study and providing sufficient information for participants to make an informed decision about their participation in this study.

The participant information sheet and the consent form will be submitted with the protocol for review and approval for the study by the CEC. The formal consent of a participant, using the approved consent form, must be obtained before that participant is submitted to any study procedure.

The participant should read and consider the statement before signing and dating the informed consent form, and should be given a copy of the signed document. The consent form must also be signed and dated by the investigator (or his designee) and it will be retained as part of the study records.

## **1.13 Participant Privacy and Confidentiality**

The investigators are liable to treat the entire information related to the study and the compiled data strictly confidentially. Any passing-on of information to persons that are not directly involved in the study must be approved by the owner of the information.

Data generation, transmission, archiving and analysis of personal data within this study, strictly follows the current Swiss legal requirements for data protection. Prerequisite is the voluntary approval of the Participant given by signing the informed consent prior start of participation of the clinical trial.

Individual participant medical information obtained as a result of this study is considered confidential and disclosure to third parties is prohibited. Participant's confidentiality will be further ensured by utilizing participant identification code numbers to correspond to treatment data in the computer files.

Such medical information may be given to the participant's personal physician or to other appropriate medical personnel responsible for the participant's welfare, if the patient has given his/her written consent to do so.

Data generated as a result of this study are to be available for inspection on request by the monitors and by the CEC.

## **1.14 Early Termination of the Study**

The Sponsor-Investigator may discontinue the study prematurely according to certain circumstances:

- ethical concerns,
- insufficient participant recruitment,
- when the safety of the participants is doubtful or at risk, respectively,
- alterations in accepted clinical practice that make the continuation of a clinical trial unwise,
- early evidence of benefit or harm of the experimental intervention

## **1.15 Protocol Amendments**

Substantial amendments (significant changes) are only implemented after approval of the CEC.

Significant changes to be authorized by the CEC are the following:

- changes affecting the participants' safety and health, or their rights and obligations;
- changes to the protocol, and in particular changes based on new scientific knowledge which concern the trial design, the method of investigation, the endpoints or the form of statistical analysis;
- a change of trial site, or conducting the clinical trial at an additional site; or
- a change of sponsor, coordinating investigator or investigator responsible at a trial site.

Under emergency circumstances, deviations from the protocol to protect the rights, safety and well-being of human participants may proceed without prior approval of the sponsor and the CEC. Such deviations shall be documented and reported to the sponsor and the CEC as soon as possible.

All Non-substantial amendments are communicated to the CEC within the Annual Safety Report (ASR).

# **2 INTRODUCTION**

## **2.1 Background and Rationale**

The use of orthopedic implants has been steadily increasing over the last 50 years. Despite considerable technical progress, including perioperative skin disinfection and antibiotic prophylaxis, implant-associated infections remain a feared complication. Infection rates up to 2% after primary joint arthroplasties (Tande and Patel 2014) have been described. National data published by Swissnoso – the National Center for Infection Prevention –reported an infection rate of 1.2% in hip arthroplasties (Vergleichsbericht 2015/2016). Considering an infection rate of up to 1.2%, 400 surgeries with primary hip arthroplasty implantation at the Orthopedic Department of

the Balgrist University Hospital (data of 2015) would result in five periprosthetic joint infections (PJI) per year, which is medically highly relevant regarding morbidity, mortality and estimated costs of 225'000 CHF in total.

Because bacteria grow and persist in biofilms on the implant surface such infections are difficult to eradicate. Definite cure of biofilm infections requires adequate surgical debridement and prolonged treatment with an antimicrobial agent resulting in high health-care costs (Tande and Patel 2014). Most commonly isolated microorganisms in implant-associated infections are staphylococci, streptococci, enterococci, Gram-negative bacteria, and anaerobic bacteria such as *Cutibacterium acnes/avidum* (formerly *Propionibacterium acnes/avidum*) (Tande and Patel 2014).

The majority of implant-associated infections are acquired during surgery. It is hypothesized that the same bacteria that colonize the skin surface contaminate the orthopedic implant and cause acute or chronic infections (Pulido, Ghanem et al. 2008). Prevention of implant-associated infections is key to avoid re-operations and prolonged antibiotic treatment. Current preoperative prevention strategies are multifaceted with the focus on skin antisepsis and single shot of an antibiotic within 30-60 minutes before surgery (Bratzler, Dellinger et al. 2013, Dumville, McFarlane et al. 2015). Preoperative skin disinfection is performed with alcoholic povidone-iodine (PVI) or chlorhexidine gluconate (CHG) prior to implantation as a standard skin preparation (Dumville, McFarlane et al. 2013, Berrios-Torres, Umscheid et al. 2017). Povidone iodine oxidizes cell constituents and inactivates proteins by iodinating them. Regarding the skin commensal *Cutibacterium acnes*, it could be shown that despite administration of standard preoperative prophylaxis before shoulder arthroplasty surgeries, *C. acnes* could be detected in different sample types (in dermis, fascia, synovium, and glenoid tissue of shoulder) of 3 out of 10 patients without any signs of infection (Matsen, Russ et al. 2015). There is an increasing number of studies reporting the presence of bacteria in deep tissue, which is commonly considered as sterile. A recent study by Lee et al. found viable *C. acnes* in the dermal tissue in seven out of 10 male volunteers after surface skin antisepsis (Lee, Pottinger et al. 2014). All these study results have led to the assumption that not only the superficial skin bacteria but also bacteria in the dermis may find the way to deeper structures and infect an implant.

We hypothesize that local photodynamic treatment (PDT) is able to reduce persistent skin colonizing bacteria through the destruction of the sebaceous and sweat glands as well through bactericidal effects and thus improve skin antisepsis before surgical incision and implantation of foreign material leading to a lower rate of surgical site infections. The aim of this pilotstudy in maximum 20 participants within a year is to evaluate the effect of PDT on colonizing bacteria immediately before surgical skin antisepsis and after it (1 and 3 weeks later). If we see promising results in this pilotstudy, we will plan a prospective clinical trial in patients undergoing hip arthroplasty surgery.

## 2.2 Study Intervention and Indication

Study intervention	Indication
PDT	
 
- Bactericidal effect on skin bacteria
 
- Destruction of sebaceous and sweat glands
 

Skin swabs	
 
- To measure bacterial growth of colonizing bacteria
 

Skin biopsies in 5 participants	
 
- To measure growth of persistent bacteria in
 

	

- sebaceous and sweat glands (Microbiology)

- To analyze skin/dermis structure including size of sebaceous and sweat glands (dermatohistopathology)

--	---

## 2.3 Clinical Evidence to Date

Photodynamic treatment (PDT) has recently gained attention in the treatment of acne, a disease of the pilosebaceous unit, in which also *C. acnes* is implicated. The PDT works here on the one hand through a longlasting destruction of the sebaceous glands, and on the other hand due to anti-inflammatory and antimicrobial effects (Sakamoto, Lopes et al. 2010). In following studies, photodynamic therapy not only validated its efficient activity against bacteria involved in acne such as *C. acnes*, it showed also activity against various other classes of microorganisms (Awad, Tovmasyan et al. 2016). The mechanism of action of the PDT is a photochemical reaction through the generation of reactive oxygen species in the presence of oxygen, mainly excited singlet oxygen, by a non-toxic-photosensitizer reacting with visible light. Photodynamic treatment is routinely performed among others for non-melanoma skin cancer and therapy-refractory inflammatory dermatoses at the Department of Dermatology at the University Hospital Zurich. The treatment enjoys great popularity as it is well tolerated, can be repeated arbitrarily often, and gives excellent cosmetic results.

## 2.4 Justification of Study Intervention

Skin swabs and small skin biopsies have only minimal risks and the PDT enjoys great popularity as it is well tolerated. Therefore, we select this promising treatment to investigate an innovative strategy to improve skin antisepsis in a pilotstudy. If we see that we have sterile cultures after PDT and skin antisepsis we will plan a larger prospective study based on these data.

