## 2.5 *Explanation for Choice of Comparator Intervention*

Not applicable, study without PDT is currently ongoing (study acronym DESCAY, ethical number 2018-00783) at the Orthopedic University Hospital Balgrist. The results of this prospective study will be used as reference for this pilot study results.

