#### **Study schedule:**

On day 0 with [name] and [name], a skin scraping of the groin will be performed and sent for microbiological culture. Then, 5% topical methyl aminolevulinate (MAL) as the photosensitizer will be applied for 3 hours under occlusion in the right groin of the patient. After the incubation, the photodynamic process will be started by irradiation of the area with 40J/cm^2 red light from a 633nm emitting LED during 13 minutes.

Immediately after the MAL-PDT, skin antisepsis will be performed. Antisepsis of the skin is performed with a povidone-iodine/alcohol solution (Betaseptic®, Mundipharma, Limburg, Germany) and repeated three times for a total duration of 3 minutes to imitate standard surgical antisepsis before a hip arthroplasty surgery. Skin scraping will be repeated after the 3rd antisepsis and 7 and 21 days later (study visit day 7 and 21) for bacterial cultures.

As a control group, we will take skin swabs before and after skin antisepsis without PDT in 10 participants.

On day 35 ( $\pm 7$  days) of the study, volunteers will be seen for the last study visit to document any adverse effects and to inform about the individual study result.

Substudy in 5 volunteers:

In the course of the study a total of three small skin biopsies are taken (3mm diameter each) from 5 volunteers. The time and locations of the performed biopsies will be

1. from the right groin immediately after the MAL-PDT or at day 7
2. from untreated control area in the left groin after the MAL-PDT (day 0 or 7)
3. from the MAL-PDT area on day 21 as the control after treatment.

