## 6 STUDY POPULATION

Twenty healthy male and female volunteers'  $\geq 18$  years will be recruited for this clinical study. With the results of an ongoing trial investigating the effect of skin antisepsis before hip arthroplasty, we have a perfect comparator intervention group without the PDT intervention. An expected enrolment goal is 2-4 participants per month.

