#### 7.1.2 Control Intervention

No control intervention in this study

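### The only concrete trigger for the larger trial, culture sterility in the PDT group, has no cut-off and does not use the antisepsis-only controls already planned

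*Combined protocol and SAP*

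**What the plan says.** The decision to go on to a trial in hip arthroplasty patients is worded in four places.

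- Section 2.4: "If we see that we have sterile cultures after PDT and skin antisepsis we will plan a larger prospective study based on these data".
- Section 2.1, repeated in Section 5.1: "If we see promising results in this pilotstudy, we will plan a prospective clinical trial in patients undergoing hip arthroplasty surgery". What counts as promising is not defined.
- Synopsis, number of participants: "There will be only descriptive statistics to see if numbers of colonizing bacteria are decreased with photodynamic treatment to plan a clinical trial". Here fewer bacteria would do; sterility is not required.

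On a comparator, the study schedule in Section 5.2 says: "As a control group, we will take skin swabs before and after skin antisepsis without PDT in 10 participants". The synopsis describes the same group but says it goes without antisepsis, which cannot be meant. An ongoing external study without PDT is also brought in. Section 2.5 says "The results of this prospective study will be used as reference for this pilot study results", and Section 6 says "we have a perfect comparator intervention group without the PDT intervention". Section 7.1.2, however, says "No control intervention in this study".

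Group sizes are not settled. Section 7.1.1 has 20 participants receiving PDT, a footnote to Figure 1 in Section 5.2 implies a group of 10, and Section 6.3 names 10 to 15 as the minimum. Section 10.2 gives 20 without a calculation. The primary analysis in Section 10.3.2 is a descriptive comparison before versus after PDT and does not mention the controls.

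**The concern.** The pilot's main product is the decision whether to run the arthroplasty trial. The post-procedure scraping is taken after two antibacterial steps, PDT and then three rounds of povidone-iodine/alcohol. A sterile culture at that point may be the work of either. Only the result of antisepsis without PDT can tell them apart, and the decision wording does not call on it.

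The wording also leaves open how many cultures must be sterile. In an open-label study that reports individual results to volunteers at day 35 (Section 8.3.5), a threshold chosen after the cultures are known could make almost any result count as a pass or a fail.

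**Working it through.** **Nothing to reproduce.** No rate, effect size, power or threshold stands behind the 20 volunteers, so the check is on how the go criterion behaves.

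**Step 1: does any passage tie the decision to a control?** None of the four wordings names a comparator. Section 10.3.2 compares before with after PDT. For the immediate effect, item 1.1 of Section 3.2 places the later sample after both PDT and antisepsis. The planned before-after change therefore includes the antisepsis effect.

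**Step 2: inputs.**
- Number treated, n: 10 (Figure 1 footnote) or 20 (Section 7.1.1).
- Sterile share after antisepsis alone: not given for groin scrapings. Section 2.1 cites *C. acnes* in 3 of 10 shoulder arthroplasty patients and in the dermis of 7 of 10 volunteers. That is at most 70% and 30% sterile. These are one species in shoulder or dermal samples, so I use 30% and 70% only as an assumed range.
- Sterile share with a useful PDT: 90%, an assumption.
- Participants independent, one culture each. Several cultures per person would make the all-sterile reading stricter.

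**Step 3: chance that the criterion is met.** With X sterile cultures, X ~ Binomial(n, s), and r the number required, the chance of passing is P(X ≥ r). For at least one it is 1 − (1 − s)^n; for all it is s^n. A PDT that adds nothing has s equal to the background.

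| Reading | n | s = 30% | s = 70% | s = 90% |
|---|---|---|---|---|
| At least one sterile | 10 | 97.2% | >99.9% | >99.9% |
| At least one sterile | 20 | 99.9% | >99.9% | >99.9% |
| Majority (6 or more) | 10 | 4.7% | 85.0% | 99.8% |
| Majority (11 or more) | 20 | 1.7% | 95.2% | >99.9% |
| All sterile | 10 | <0.01% | 2.8% | 34.9% |
| All sterile | 20 | <0.01% | 0.08% | 12.2% |

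For example, 1 − 0.70^10 = 1 − 0.028 = 97.2%. Likewise 0.90^10 = 34.9%, so a PDT at 90% sterility fails 65% of the time; 0.90^20 = 12.2%, so it fails 88%. To pass the all-sterile reading half the time, the true sterile share must be 0.5^(1/10) = 93.3% (n = 10) or 0.5^(1/20) = 96.6% (n = 20).

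**Step 4: what an all-sterile result would show.** The exact 95% upper limit for growth when none is seen is 1 − 0.025^(1/n): 30.8% for 0/10 and 16.8% for 0/20.

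**Step 5: what the planned controls can deliver.** Exact enumeration of Fisher's test at two-sided 0.05:

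| PDT v control | 90% v 30% sterile | 90% v 70% sterile | Rejection with no difference (either direction) |
|---|---|---|---|
| 10 v 10 | 66.7% | 5.7% | 1.2% |
| 20 v 10 | 92.3% | 22.6% | 3.1% |

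The contrast addresses attribution. Used as a significance test it has little power if antisepsis alone already leaves about 70% sterile.

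**The case against.** The strongest reply is that the comparator exists. A reader might infer that the study has no antisepsis-only result to judge PDT against. The documents do not support that: 10 controls are planned, and Section 2.5, directly after the go sentence, names an external reference. What stands is that the decision wording uses neither. The external study is in arthroplasty patients, and Section 5.3 concedes that the volunteers' microbiome may differ from theirs. Section 8.3.2 also lists a scraping between PDT and antisepsis. That could show what PDT does alone, but not what it adds to the post-antisepsis result.

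A reader might also infer that the rule is all-or-nothing, and so both lets a useless PDT through and usually fails a useful one. That goes too far. Section 2.4 does not say that all cultures must be sterile. On the all-sterile reading, a PDT that adds nothing passes often only if antisepsis alone is already near-sterile: 35% at 90% sterile and 60% at 95% (n = 10). The synopsis says that antisepsis does not eliminate skin bacteria, which fits poorly with such a background, although it gives no rate. Under any single cut-off the pass chance rises with the sterile share, so a useless PDT never passes more often than a useful one.

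Nor do the figures support a general claim that sterile cultures could not exclude the persistence rates cited in Section 2.1. 0/20 excludes both 30% and 70%. 0/10 excludes 70% and only narrowly fails to exclude 30%.

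Finally, the go sentence is a statement of intent in a justification section of a pilot that Section 10.3 calls descriptive. That lowers the severity but does not remove the attribution problem.

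**Conclusion.** The concern holds in this form: the one concrete go criterion has no cut-off and leaves out the planned antisepsis-only control, and the decision is worded differently elsewhere. Sterility in the PDT group alone cannot be credited to PDT; this follows from the text and needs no assumed rate.

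The size of the problem depends on the reading. Lenient readings pass a PDT that adds nothing in 97% (at least one sterile, 30% background) or 85% (majority, 70% background) of studies at n = 10. The strict reading fails a PDT reaching 90% sterility in 65% (n = 10) or 88% (n = 20). These opposite errors belong to different readings and should not be presented as both true of one rule. They rest on assumed sterile shares of 30%, 70% and 90%, and on independent participants with one culture each.

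This should be fixed, but for a statement of intent in a descriptive pilot it is not a must-fix.

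**What to change.** Replace the go wording in Sections 2.1, 2.4 and 5.1 and in the synopsis with a single rule:

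- **Measure:** the share of participants with bacterial growth in the day-0 scraping after antisepsis, PDT group minus concurrent antisepsis-only group, with an exact 95% confidence interval.
- **Threshold:** the smallest difference that would justify the larger trial, written down before any culture result is tabulated by group.
- **Explicit exclusion:** sterile cultures in the PDT group alone do not trigger the larger trial.

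Name this contrast in Section 10.3.2. Reconcile the synopsis, Section 5.2 (text and Figure 1 footnote), Section 7.1.1 and Section 7.1.2 on whether there is a control group, what it receives, how many are in each group, and whether the 10 controls are part of the 20. State how controls are chosen, since the text does not and the contrast depends on it.

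The cost is protocol wording, with no added visits or samples if the controls in Section 5.2 go ahead. Section 1.15 counts changes to design, endpoints or statistical analysis among those needing ethics approval, so an amendment may be required. The downside is a wide interval. With about 6% power at 10 v 10 for 90% v 70% sterile, the rule should rest on the estimate and its interval, not on significance.
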